## **D. Background**

From a neurophysiological point of view, maintaining balance is a complex function, especially in the high instability of one-foot support (monopodal support). It requires the integration of many systems for the collection of information (vestibular apparatus, proprioception, baroception, sight), for the processing of the information itself (carried out by the central nervous system - CNS, with particular contribution from the cerebellum), and for the activation and management of the responses to be given (through the muscles) (Horak, 1986; Winter, 1995; Adkin, 2000; Wang, 2014).

The "static" monopodal posture (i.e. in a position that is as still as possible), with the drastic reduction of the support base that it entails, undermines the balance maintenance system and generally requires significant muscle activation with consequent energy expenditure.

For this reason, it is widely used to evaluate and train the balance itself. In the literature, it has been extensively analyzed for therapeutic exercise, functional assessment and sports training (Katayama, 2004; Chang, 2005; Granacher, 2011; Greenwood, 2011; Pfusterschmied, 2013; Brachman, 2017; Alfuth, 2017; Rahman, 2017). The goals are to test and/or increase balance, proprioception, strength and muscle endurance. A major issue concerns the prevention of falls in the elderly (Donath, 2016; Kurz, 2018; Granacher, 2011; Muehlbauer, 2015).

Another aspect of interest linked to the analysis of monopodal support is the study of the strategies for maintaining balance and stabilization of the joints (Kristensen, 2016; Wolburg, 2016; Mirzaie, 2019; Kurz, 2018).

Numerous studies in the literature have examined static monopodal equilibrium, taking into account different experimental conditions and outcome measures. Usually, with regard to muscle activity, the average intensity of activation and response latency were measured (Greenwood, 2011; Dingenen, 2015; Donath, 2016; Wolburg, 2016; Alfuth, 2017; Rahman, 2017; Mirzaie, 2019; Kurz, 2018). A distinction has never been made, however, between activities related to medial and lateral imbalances respectively, if not at the level of the ankle (Morey-Klapsing, 2005). There is therefore no global approach, which involves at least the entire lower limb, and evaluates in detail the motor strategies used by the body to obtain balance.

## **E. The Study**

Hypothesis and rationale. Colonna (2012) assumes, basing on the interpretative approach of myofascial chains, that the management of balance occurs through the anterior and posterior spiral chains. According to the myofascial chain approach, muscles are no longer considered independent, but connected in series via the connective tissue (muscle fascia, tendons, ligaments, ...). The concept of myofascial chains suggests that mechanical force can be transferred not only within a limb between synergistic or antagonistic muscles, but also between muscles arranged in series (Wilke, 2018).

Colonna's hypothesis, which has never been experimentally verified, is based on the intuitive search for the most effective system to respond to the perturbations that destabilize the equilibrium. The "cruciate" system that the spiral chains form in the lower limb appears to be the most appropriate response, as it is more stabilizing.

This preliminary study is not intended to provide direct treatment indications. It is therefore not a study aimed at clinical practice.

The aim is to carry out a preliminary study to test the reasonableness of the hypothesis that the spiral myofascial chains intervene in the monopodal equilibrium, verifying the feasibility of the proposed method to analyze the response to a medial and lateral imbalance.

The results of this study will be used to determine the opportunity for future investigations (with statistically significant number of subjects, assessment of muscle activation variations as a function of different pathologies, etc.) and the eventual definition of an optimal experimental setting and methodology.

#### **F. Study design.**

Setting: preliminary experimental

Type: non-pharmacological

Organization: monocentric

Enrollment: consecutive

Conduction: open

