#### **H. Outcome measures**

The core of the study consists in carrying out a measurement of activation of the muscles of the lower limb. In particular, it will be necessary to measure this activation as a response to an imbalance / perturbation in monopodal stance.

Muscle activity will be evaluated for 1500ms, 500ms before and 1000ms after the disturbance. The early response to the stimulus will be identified in the interval of 100-500ms after the stimulus.

The muscles considered will be, for the anterior spiral chain, the adductor longus and the peroneus longus, for the posterior spiral chain, the glutei (medium and large) and the tibialis anterior. Therefore, both muscles of the thigh (glutei and adductor longus) and of the leg (peroneus longus and tibialis anterior) will be examined.

The goal is to understand which of these muscles are activated together, in particular if the muscles belonging to the same myofascial chain are activated together. The simultaneous activation will be measured with the calculation of the correlation coefficient. The hypothesis of spiral chains use for the balance will be

considered reasonable if it is possible to observe greater correlation between the peroneus longus-adductor longus and between the glutei-tibialis anterior than the correlation between the glutei-peroneus longus and between the tibialis anterior- adductor longus.

The outcome measures will therefore be:

- Maximum intensities of early activation, normalized with respect to the electrical intensity measured in the maximal contraction, respectively in response to a stimulus that causes a medial and lateral imbalance;
- Correlation coefficients between the electrical activities of:
  - adductor longus-peroneus longus
  - glutei-tibialis anterior
  - glutei-peroneus longus
  - adductor longus-anterior tibialis

in response to a stimulus that causes medial imbalance;

- Correlation coefficients between the electrical activities of:
  - adductor longus-peroneus longus
  - glutei-tibialis anterior
  - glutei-peroneus longus
  - adductor longus-anterior tibialis

in response to a stimulus that causes lateral imbalance.

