### *Measurement protocol*

The analysis will be carried out on the right lower limb of each subject.

The electromyographic devices will be applied to the tibialis anterior, peroneus longus, gluteus medius, gluteus maximus and adductor longus.

The reflective markers will then be applied (using double-sided tape) according to the Total3DGait protocol, which identifies the body segments of the forearms, arms, trunk, pelvis, thighs, legs, and feet.

The subject must position himself with his right foot on a force platform.

The toe of the left foot will be allowed to rest on the ground (on the other power platform placed at the rear), with the verbal indication to load as little weight as possible on it: this indication is aimed at reducing muscle activation in the absence of external perturbations, in order to highlight only the activity caused by the perturbations themselves. Only acquisitions in which the load on the left foot will be less than 30% of the weight will be considered valid.

The hands will be placed on the hips to limit the variables to be controlled and to standardize the posture, in order to focus the contribution to the balance of the lower limb. The left thigh has to be kept vertical. Finally, it will be required to find, within the constraints described above, the posture that is as comfortable as possible, with minimal muscle contraction. The distance between the feet is therefore freely chosen by each subject.

The operator positions himself behind the subject to be examined, and without being seen performs lateral thrusts with the medial margin of the hand at the proximal third of the thigh. At least ten pushes per side will be performed, with random timing. The thrusts will be quick but without causing pain.

The operator will then request maximal contractions from the subject, in order to normalize the electrical activity of each muscle with respect to its maximum. It will be required to perform the dorsiflexion and pronation of the foot against resistance, then the adduction, abduction and extension of the hip.

The whole procedure takes about an hour.

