### *Data processing*

Electromyographic signals are processed in the following way:

- high pass filter: to eliminate any disturbances (movement artifacts) and keep only the high frequency signal typical of muscle activity;
- rectification: the signal, which is an oscillation around zero, is taken only as an absolute value;
- envelope: application of the Root Mean Square on a span of 200ms (before and after) and moving average, to quantify the extent of muscle activation;

- normalization: muscle activation is normalized with respect to the maximum contraction value; it is therefore expressed as a percentage of this value;
- median: for each muscle of each subject the median of the different response activations is calculated; the median, once a series of values has been placed in ascending order, is constituted by the central value; compared to the average, it allows to reduce the influence on the final value of the most anomalous cases compared to the majority;
- correlation coefficient: calculation of the correlation coefficient to verify any synergies present between the different muscle groups.

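### Signal processing is unmasked and several settings are left open, while the criterion changes sign when two leg-muscle labels are swapped; coding those two channels until the settings are locked is a near-costless safeguard.

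*Combined protocol and SAP*

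**What the plan says.** - **Conduct.** Section F gives one line: "Conduction: open". Sections H, I and K mention no masking of the person who processes the signals.
- **Criterion.** Section H sets the bar for the spiral-chain hypothesis, which counts as "considered reasonable if it is possible to observe greater correlation between the peroneus longus-adductor longus and between the glutei-tibialis anterior". These two within-chain pairs are set against two cross-chain pairs: peroneus longus with the glutei, and adductor longus with tibialis anterior. The same four correlations are listed separately for medial and for lateral imbalance.
- **Muscles.** The hip and thigh side is the glutei and adductor longus; the other side is described by "of the leg (peroneus longus and tibialis anterior) will be examined".
- **Pushes.** Section I, Measurement protocol: "At least ten pushes per side will be performed, with random timing". They are delivered by the operator's hand. The one validity rule is numeric: "Only acquisitions in which the load on the left foot will be less than 30% of the weight will be considered valid".
- **Processing.** Section I, Data processing, lists filtering, rectification, envelope, normalisation, median and correlation. The filter step reads "high pass filter: to eliminate any disturbances (movement artifacts) and keep only the high frequency signal typical of muscle activity", with no cut-off.
- **Inference.** Section K plans no significance calculations and looks for an indicative trend in 5 subjects. Section E says the results will inform whether further studies are worthwhile.

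**The concern.** The output of the study is a direction: do the within-chain correlations exceed the cross-chain ones? With no test or interval, nothing downstream would show that the direction came from processing choices rather than from the muscles. Several of those choices are not settled in the protocol, and nothing prevents their being made with the muscle names in view.

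The criterion has a useful property. Whether a choice favours or opposes the hypothesis depends on which of two channels is called peroneus longus and which tibialis anterior. Someone who knows the labels can tell which way a choice pushes the answer; someone who does not know them cannot. Without coding, the direction that informs the decision on further studies could be partly produced by the processing.

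**Working it through.** **1. Effect of swapping the two leg labels.** Write AL = adductor longus, PL = peroneus longus, TA = tibialis anterior, G = glutei, and from section H:

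- within chain: a = r(AL, PL), b = r(G, TA)
- cross chain: c = r(G, PL), d = r(AL, TA)

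The averaged contrast is D = (a + b − c − d)/2. This average is one reading of section H, which does not say how the comparisons are combined. Exchanging PL and TA turns a into d, d into a, b into c and c into b, so D′ = (d + c − b − a)/2 = −D. In 1,500 simulated data sets the largest |D + D′| was about 2 × 10⁻¹⁶, that is, zero.

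On the strict reading (both within-chain values exceed both cross-chain values) the four correlations have 4! = 24 orderings without ties:

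| Outcome | Orderings |
|---|---|
| Rule met | 2! × 2! = 4 |
| Rule met only after the swap | 4 |
| Met neither way (mixed) | 24 − 8 = 16 |

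A fully met rule always turns into its opposite. A mixed result stays mixed.

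**2. What is open before the correlations are computed.**

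| Step | Given | Not given |
|---|---|---|
| Push onset | Window from −500 to +1000 ms around it (H) | How the instant of a manual push is found |
| Filter | High-pass (I) | Cut-off |
| Trace rejection | Left-foot load below 30% (I) | Any rule on signal quality |
| Pushes kept | At least 10 per side (I) | A fixed number |
| Glutei | Medius and maximus both recorded (I) | How the two become one signal |
| Correlation | Coefficient named (H, I) | Type, time window, per push or on the median |

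The maximal-contraction value does not belong on this list for a within-subject correlation, since r(kx, y) = r(x, y) for any k > 0. It could matter only if data were pooled across subjects, or through the weighting of the two glutei.

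**3. Illustration: best of k variants.** Assumptions, none from the documents: no true difference, k processing variants whose averaged contrasts are exchangeable normal with correlation ρ, and the most favourable one kept.

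P(best > 0) = 1 − ∫ Φ(−u√(ρ/(1−ρ)))^k φ(u) du

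For k = 2 this equals 3/4 − arcsin(ρ)/(2π). At ρ = 0.8: 0.75 − 0.9273/6.2832 = 0.75 − 0.1476 = 0.60.

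| ρ | k = 1 | k = 2 | k = 4 | k = 8 |
|---|---|---|---|---|
| 0.9 | 0.50 | 0.57 | 0.63 | 0.68 |
| 0.8 | 0.50 | 0.60 | 0.69 | 0.75 |
| 0.5 | 0.50 | 0.67 | 0.80 | 0.89 |

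**4. Illustration: dropping pushes.** Assumptions: no chain effect, 12 pushes, a 400 ms RMS window (200 ms before and after), median waveform, Pearson correlation, 1,500 runs. The extreme case lets the analyst drop whichever 2 of 12 pushes help most.

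| Handling | D > 0, per subject | D > 0 in at least 4 of 5 | Strict rule met, per subject |
|---|---|---|---|
| No selection | 0.53 | 0.22 | 0.08 |
| Selection, labels visible | 0.94 | 0.97 | 0.31 |
| Selection, PL and TA coded | 0.50 | 0.19 | 0.16 |

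The expected value without selection is 0.50 by symmetry; 0.527 lies about two simulation standard errors above it (0.027/√(0.25/1500) = 2.1). The exact figure for at least 4 of 5 at 0.50 is 6/32 = 0.19.

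The last column matters. Coded selection still doubles the strict-rule rate (0.08 to 0.16), because selecting makes any clear pattern more common. Coding removes the lean towards one side, not the effect of selecting.

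**The case against.** The strongest reply is that no hand judgement is documented. Data processing lists computed steps only, the filter is an automatic operation, and the open label in section F is a general design descriptor that does not mention signals. A reader might infer that someone edits traces by eye with the muscle names showing. The protocol does not say so: both the visible labels and the discretion are inferred from silence. That stands, and the point must rest on the open settings alone.

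The protocol also has partial safeguards. The median limits the pull of anomalous responses, and the 30% load rule is numeric. Push onset is shared by all channels, so it cannot be shifted for one muscle. These narrow the room for choice without closing it: a shared onset, or a different set of pushes, still changes all four correlations.

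A further reply is that fixing every setting beforehand would give k = 1, and so 50%, with no masking at all. This is correct, and it makes coding the secondary measure. Coding still helps where a setting cannot be fully specified before the first recordings are seen.

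Finally, this is a 5-subject feasibility study without inference. That limits the weight of the point, but the direction still informs the decision on later studies.

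**Conclusion.** The point holds as a cheap improvement. No masking is planned, several settings are open, and the criterion is antisymmetric in two labels: exactly so for the averaged contrast and for a fully met rule. Choices made with those labels known could lean towards the hypothesis.

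Three stronger readings are tempting and not supported:

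- *That the verdict always reverses.* On the strict reading, 16 of 24 orderings are mixed and stay mixed.
- *That coding would stop the bias.* The resisted dorsiflexion and pronation recordings in section I would reveal which channel is which, the trace itself may give it away, and coded selection still inflates clear patterns.
- *That the percentages estimate this study's bias.* They rest on assumed k, ρ, push numbers and analyst behaviour, and nothing in the documents suggests that variants will be tried and chosen. They show what is possible. The 50% baseline also belongs to the averaged contrast; with all orderings equally likely the strict rule gives 4/24, about 17%.

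The actual size cannot be derived from the documents.

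**What to change.** Change the conduct line in section F to: *open for push delivery; signal processing coded for the two leg muscles*. Add to Data processing:

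1. On export, a script renames peroneus longus and tibialis anterior L1 and L2, in random order for each subject, and saves the key separately.
2. Under these codes, fix and save the push onsets, filter setting, any rejected pushes, correlation window and way of combining the two glutei.
3. Extract maximal-contraction values by script, outside the coded review, so that the recordings that identify the muscles are not seen during it.
4. Only then open the key and compute the correlations and the verdict.

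Settings that can be fixed in the protocol should be fixed there as well; coding complements this. It does not cover push delivery or electrode placement.

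Cost: a short script and a key file on the laboratory PC, with no extra subjects, staff or measurements. Downside: the code may sometimes be guessed from the trace, so the protection is partial.

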#### **G. Population**

The study aims to carry out a preliminary assessment of the feasibility and reasonableness of hypotheses. The sample to be examined must therefore be composed of healthy subjects, in order to limit the variables determined by possible pathologies that alter physiological behavior. The age of the subjects must allow a full maturity of the neuro-musculoskeletal system and precede its degeneration. As this is a preliminary study, a sample size to provide statistical significance is not sought. The sample must be functional to test the method and to verify whether the hypothesized motor strategy can be detected in the subjects considered. The recruitment can be achieved through the search for volunteers among the acquaintances of the experimenters.

Number of subjects: 5

Inclusion criteria: healthy adult subjects, aged between 18 and 65 years.

Exclusion criteria: skeletal or neuromotor pathologies, past or current, which may compromise the maintenance of balance and / or modify the strategies in implementing it (in the opinion of the investigators).

#### **H. Outcome measures**

The core of the study consists in carrying out a measurement of activation of the muscles of the lower limb. In particular, it will be necessary to measure this activation as a response to an imbalance / perturbation in monopodal stance.

Muscle activity will be evaluated for 1500ms, 500ms before and 1000ms after the disturbance. The early response to the stimulus will be identified in the interval of 100-500ms after the stimulus.

The muscles considered will be, for the anterior spiral chain, the adductor longus and the peroneus longus, for the posterior spiral chain, the glutei (medium and large) and the tibialis anterior. Therefore, both muscles of the thigh (glutei and adductor longus) and of the leg (peroneus longus and tibialis anterior) will be examined.

The goal is to understand which of these muscles are activated together, in particular if the muscles belonging to the same myofascial chain are activated together. The simultaneous activation will be measured with the calculation of the correlation coefficient. The hypothesis of spiral chains use for the balance will be

considered reasonable if it is possible to observe greater correlation between the peroneus longus-adductor longus and between the glutei-tibialis anterior than the correlation between the glutei-peroneus longus and between the tibialis anterior- adductor longus.

The outcome measures will therefore be:

- Maximum intensities of early activation, normalized with respect to the electrical intensity measured in the maximal contraction, respectively in response to a stimulus that causes a medial and lateral imbalance;
- Correlation coefficients between the electrical activities of:
  - adductor longus-peroneus longus
  - glutei-tibialis anterior
  - glutei-peroneus longus
  - adductor longus-anterior tibialis

in response to a stimulus that causes medial imbalance;

- Correlation coefficients between the electrical activities of:
  - adductor longus-peroneus longus
  - glutei-tibialis anterior
  - glutei-peroneus longus
  - adductor longus-anterior tibialis

in response to a stimulus that causes lateral imbalance.

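### The verdict rule and outcome lists leave out the two same-segment, opposite-chain muscle pairs, so co-activation within a segment would go unseen and could be read as chain-specific

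*Combined protocol and SAP*

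**What the plan says.** Section H (Outcome measures) assigns the muscles to chains: "The muscles considered will be, for the anterior spiral chain, the adductor longus and the peroneus longus, for the posterior spiral chain, the glutei", together with the tibialis anterior. It also gives the body segments: "both muscles of the thigh (glutei and adductor longus) and of the leg (peroneus longus and tibialis anterior) will be examined".

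The aim, which concerns joint activation, is put broadly: "The goal is to understand which of these muscles are activated together, in particular if the muscles belonging to the same myofascial chain are activated". The rule is narrower. The hypothesis counts as reasonable if the recordings show "greater correlation between the peroneus longus-adductor longus and between the glutei-tibialis anterior than the correlation between the glutei-peroneus longus and between the tibialis anterior- adductor" (the last muscle named is the adductor longus). The correlation outcomes, listed once for medial and once for lateral imbalance, are these same four pairs.

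Section I records all the muscles involved: "The electromyographic devices will be applied to the tibialis anterior, peroneus longus, gluteus medius, gluteus maximus and adductor longus". Its data-processing step describes the "calculation of the correlation coefficient to verify any synergies present between the different muscle groups" and names no pairs. Section K plans no significance calculation. The documents give no reason for restricting the pairs.

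**The concern.** The two pairs left out are the ones within a segment: glutei-adductor longus in the thigh and tibialis anterior-peroneus longus in the leg. By section H's own assignment, each joins muscles of different chains. They bear on an obvious rival account of any result, namely that a push makes neighbouring muscles of a segment act together, with or without a spiral arrangement.

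Nothing these two pairs do enters the verdict, and nothing in the outcome lists would show it. The rule could return a favourable verdict while the most strongly coupled muscles belong to opposite chains. Section E says the results will inform whether and how to run further studies, so what the verdict can distinguish matters even in a preliminary study.

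**Working it through.** The plan gives no numerical figure to reproduce here. The check concerns which pairs are compared and what the rule can detect.

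**1. Pair count.** AL = adductor longus, PL = peroneus longus, GL = glutei (one group, as in section H), TA = tibialis anterior. Four groups give 4 × 3 / 2 = 6 pairs.

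| Pair | Chains | Segments | In rule and outcome lists |
|---|---|---|---|
| AL-PL | same | thigh-leg | yes |
| GL-TA | same | thigh-leg | yes |
| GL-PL | opposite | thigh-leg | yes, comparator |
| TA-AL | opposite | thigh-leg | yes, comparator |
| GL-AL | opposite | thigh | no |
| TA-PL | opposite | leg | no |

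Two of six, a third, are missing.

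**2. How the missing pairs bear on the contrast.** With signals standardised to unit length over one set of samples,

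(r_AL,PL + r_GL,TA) − (r_GL,PL + r_TA,AL) = ⟨AL − GL, PL − TA⟩ ≤ 2√[(1 − r_GL,AL)(1 − r_TA,PL)].

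If both missing correlations are 0.9, the bound is 2 × 0.1 = 0.20, or 0.10 per pair. At 0.5 it is 2 × 0.5 = 1.00, or 0.50 per pair. High same-segment correlation limits the size of the same-chain advantage but not its sign, and the rule asks only for the sign.

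**3. A pattern that passes wrongly.** Take same-segment 0.95, same-chain 0.90 and listed cross-chain 0.87. The eigenvalues of this matrix are:
- 1 + 0.95 + 0.90 + 0.87 = 3.72
- 1 + 0.95 − 0.90 − 0.87 = 0.18
- 1 − 0.95 + 0.90 − 0.87 = 0.08
- 1 − 0.95 − 0.90 + 0.87 = 0.02

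All are positive, so the matrix is possible. The rule is met, yet the highest correlations are between opposite chains.

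**4. How often the rule is met.** Assumptions, not in the documents: four-variate normal data, Pearson r, the true correlations shown, and 20 effective independent points per coefficient; 100,000 replicates. Section H does not say how the pairs combine, so two readings are used. Strict: each same-chain r exceeds every comparator. Mean: the averages are compared. Figures are for one subject and one push direction.

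| True r: same-chain / same-segment / listed cross-chain | Strict, 4 pairs → 6 | Mean, 4 pairs → 6 |
|---|---|---|
| 0.7 / 0.7 / 0.5 | 76% → 22% | 99.9% → 50% |
| 0.7 / 0.85 / 0.6 | 55% → 1% | 99.9% → 5% |
| 0.8 / 0.5 / 0.5 (chain pattern) | 92% → 88% | 99.8% → 99.5% |
| all equal, 0.6 | 11% → 5% | 50% → 33% |

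For the first row, 10 points give 52% → 20% (strict) and 98% → 50% (mean); 40 points give 94% → 22% and 100% → 50%.

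**5. Uniform co-contraction.** The last row is chance. With all correlations equal, the three ways of splitting the muscles into two pairs are interchangeable, so the mean reading passes 1/2 of the time against one comparator set and 1/3 against two. Across true values of 0.3 to 0.8 and 8 to 40 points, the strict reading passes 11-13% with four pairs and 4-6% with six. With a single common drive and positive loadings, the strict rule cannot hold in the true correlations: AL-PL above TA-AL needs PL > TA, while GL-TA above GL-PL needs TA > PL. The mean reading can hold if loadings differ: AL = PL = 0.9 and GL = TA = 0.6 give (0.81 + 0.36)/2 = 0.585 against 0.54.

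**6. Crosstalk in the leg pair.** Assume each leg electrode also picks up 30% of the other leg signal, with true same-chain r = 0.8 and all others 0.5. Each mixed signal has variance 1 + 0.09 + 2 × 0.3 × 0.5 = 1.39. Then:
- TA-PL = (0.5 × 1.09 + 0.3 × 2)/1.39 = 0.82
- same-chain = (0.8 + 0.3 × 0.5)/√1.39 = 0.81
- listed cross-chain = (0.5 + 0.3 × 0.8)/√1.39 = 0.63
- GL-AL stays at 0.50

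**The case against.** The planned contrast is coherent. All four listed pairs link thigh and leg, so it varies chain membership while holding anatomical separation roughly constant. Section E presents force transfer along muscles in series as additional to transfer between synergists or antagonists; it does not say that serial coupling must be the stronger. Same-segment coupling is thus compatible with the hypothesis, and requiring same-chain pairs to beat it would test a stricter claim than the plan makes. Crosstalk adds to this: under the leakage assumed above, a pair-by-pair requirement would reject a genuine chain pattern that the planned rule detects. These arguments stand, and they are reasons to keep the planned rule.

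It can also be said that the data-processing step is worded broadly, that the signals will exist anyway, that maximum early activation by push direction would show opposing muscles firing together, and that a five-subject preliminary study plans no inference. These carry less weight. General wording does not put the two coefficients in the outcome list, maximum intensities are not correlations, and waiving significance does not waive the stated rule. The gap concerns which pairs are examined, so more subjects would not close it.

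A reader might infer that general co-contraction of the whole limb would count as support for the chains. The documents do not support that. Such a pattern raises the two cross-chain comparators already in the rule as much as the same-chain pairs. What passes then is chance, or unequal loadings under the mean reading; adding pairs reduces chance passes without removing them. Nor do the documents call both omitted pairs antagonists: the maximal contractions in section I imply opposed actions at the hip, but nothing similar is stated for tibialis anterior and peroneus longus.

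**Conclusion.** The point holds in a limited form. Two of the six group pairs are absent from the rule and the outcomes, so the stated goal can be answered only in part. Within-segment co-activation that matches or exceeds same-chain coupling, with the listed cross-chain pairs lower, would go unseen and the result could be read as chain-specific.

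The percentages depend on assumed correlations, normal data, an assumed number of effective points and the two readings of the rule; the documents fix none of these. The six-pair figures treat both omitted pairs as full comparators, which goes further than the change recommended here. They show how much information those pairs carry, and are not the expected performance of a new rule. The pair count and the possible matrix in step 3 need no such assumptions about sampling.

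**What to change.** In section H, add glutei-adductor longus and tibialis anterior-peroneus longus to the correlation outcomes for both push directions, so that all six coefficients are reported for each subject. Keep the thigh-leg contrast as the rule. State before data are seen that, if the same-segment pairs correlate as strongly as or more strongly than the same-chain pairs, the result will be described as not distinguishing spiral-chain organisation from within-segment co-activation. Add that crosstalk can inflate the tibialis-peroneus value, so that this pair alone should not overturn the verdict.

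The cost is two more coefficients per subject and direction, or 2 × 2 × 5 = 20 in all, from signals already recorded, plus a few sentences of text. The price in interpretation is a more cautious conclusion when the same-segment values are high.
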